**Aim #1 - Hypothesis #1 (primary):** Stroke caregivers who receive the intervention will have less depressive symptoms at 1 and 12 weeks post-intervention compared to stroke caregivers in the standard care group. Our primary endpoint is the caregiver depressive score. The focus of the primary analysis will be to examine the effect of the intervention based on “intention to treat.” Data from all the participants will be part of the primary analyses regardless of actual number of completed sessions. As an exploratory study element, we will assess compliance and attempt to determine its effect on study results. For the primary analysis, the general linear mixed model for repeated measures will be used to model the follow-up depression times (1 and 12 weeks post-intervention), adjusted for baseline scores as fixed effects. Let  $y_{ij}$  be the depression score for person  $i$  at time  $j$ , then basic fixed effects model will be:

$$E(y_{ij}) = \beta_0 + \beta_1 \text{Baseline}_i + \beta_2 \text{Time}_{ij} + \beta_3 \text{Group}_i + \beta_4 \text{Group}_i * \text{Time}_{ij}$$

with covariates for baseline depression (Baseline), time (Time=0 for 1 week, 1 for 12 weeks post-intervention), and group (0 if active control, 1 if intervention). In order to control for possible chance sample imbalances resulting from randomization, the model will include covariates for baseline prognostic factors (e.g., discharge from hospital, community living center, or rehabilitation facility; caregivers’ relationship to Veteran; number of previous strokes among Veterans, etc.), deemed to have significant relationships with response and groupwise imbalances. Thus, analyses will be able to compare the groups on the measure of interest while controlling for these factors. The primary outcome of interest will be the immediate post-intervention effect at 1-week post-intervention with the 12-week post-intervention as a secondary outcome. This will be tested based on linear contrast  $\beta_3 + \beta_4$  at two-sided 0.05 level. All tests will be performed at the  $\alpha=0.05$  significance level. The correlation among observations from the same person will be accounted for through the inclusion of a random person effect into the mixed model analysis.

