**Aim #2 - Hypotheses #2 (secondary):** Stroke caregivers who receive the intervention will have superior outcomes (i.e., less burden, better problem solving skills, greater self-efficacy, and better HRQOL,) at 1 and 12 weeks post-intervention than caregivers in the standard care group. The analysis plan for Hypothesis 2 will closely follow the plan outlined above for Hypothesis 1 for each secondary outcome of interest.

**Aim #3 - Hypotheses #3 (secondary):** Veterans whose caregivers receive the intervention will have better functional abilities at 1 and 12 weeks post-intervention and less healthcare utilization at 12 weeks post-intervention measures compared to Veterans whose caregivers are in the standard care group. Since the score for the Stroke Impact Scale can be treated as a continuous, the analysis plan follows exactly as above in Hypothesis 1. Since the Veteran healthcare utilization measures are count data, the models will be a somewhat different. There will be no baseline covariates added to the model, as they are not applicable to the count measures. Analyses will be conducted for the period following baseline to 12 weeks post-intervention assessments. Generalized linear models for count data (such as Poisson or negative binomial regression models, depending on the presence or absence of over-dispersion) will be employed to determine the group effects on healthcare utilization. Log link functions will be employed on the count data to create the correct distributional data forms. As before, in order to control for possible sample imbalances resulting from randomization, all models will include covariates for prognostic factors deemed to have significant relationships with response and significant groupwise imbalances. Thus, analyses will be able to compare the groups on the measures of interest while controlling for these factors.

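### The only contrast named for the primary test, β3 + β4, is the 12-week group effect under the plan's own coding; no test is specified for the declared primary 1-week effect.

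*Combined protocol and SAP*

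**What the plan says.** All the relevant statements are in section 6 (Research Plan), Data Analysis.

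- **Model.** Under Aim #1, Hypothesis #1, the 1-week and 12-week CES-D scores are the outcomes and the baseline score is a covariate: E(y) = β0 + β1 Baseline + β2 Time + β3 Group + β4 Group×Time. A random person effect handles the within-person correlation.
- **Coding.** "time (Time=0 for 1 week, 1 for 12 weeks post-intervention"; "group (0 if active control, 1 if intervention".
- **Ranking of time points.** "The primary outcome of interest will be the immediate post-intervention effect at 1-week post-intervention with the 12-week post-intervention as a secondary outcome".
- **Test.** The sentence that follows reads "This will be tested based on linear contrast $\beta_3 + \beta_4$ at two-sided 0.05 level".
- **Other outcomes.** For burden, problem solving, self-efficacy and quality of life, "The analysis plan for Hypothesis 2 will closely follow the plan outlined above for Hypothesis 1 for each secondary outcome of interest". The Stroke Impact Scale under Aim #3 is also to be analysed exactly as in Hypothesis 1.

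No other contrast is named anywhere in the document.

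**The concern.** The ranking sentence and the test sentence do not fit together. The first makes 1 week primary. The second names a combination of coefficients that, under the stated coding, describes 12 weeks.

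An analyst who takes the contrast literally would report the 12-week p-value as the trial's primary result. An analyst who goes by the ranking sentence would report the p-value for β3. The two can reach opposite conclusions from the same data. Because the text supports both, the choice could also be made after the results are known. The single confirmatory test should leave no such room.

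**Working it through.** **Step 1: what each coefficient means.** Inputs are the model and coding under Hypothesis #1. Subtract the expected score at Group = 0 from that at Group = 1, holding Baseline and Time fixed:

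E(y | Group = 1) − E(y | Group = 0) = β3 + β4 × Time

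| Visit | Time | Group difference | Rank in the plan |
|---|---|---|---|
| 1 week | 0 | β3 | primary |
| 12 weeks | 1 | β3 + β4 | secondary |

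Numerical check with β3 = −3.1 and β4 = +2.0 (arbitrary values): the difference is −3.1 at 1 week and −3.1 + 2.0 = −1.1 at 12 weeks. The named contrast gives −1.1. Extra covariates and the random person effect do not alter this.

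**Step 2: the plan's own sample-size figure.** Inputs from the Sample Size and Power Analysis paragraph: difference 3.1, SD 8.9, two-sided 5%, power 80%, dropout 10%.

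n per arm = 2 × (1.960 + 0.842)² × 8.9² / 3.1² = 129.4, rounded up to 130

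130 / 0.90 = 144.4, rounded up to 145

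This reproduces the stated 145 per group. So 130 completers per arm is the design basis for a test at one time point.

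**Step 3: what the two contrasts can detect.** The documents do not say how the effect changes from 1 to 12 weeks, so the fraction retained is an assumption, shown over its range. The standard error of a group difference at one visit is 8.9 × √(2/130) = 1.104. Power is for a two-sample t-test, two-sided 5%, 130 per arm, with a 1-week effect of 3.1 points throughout.

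| Effect left at 12 weeks | Points | Power of β3 (1 week) | Power of β3 + β4 (12 weeks) |
|---|---|---|---|
| All | 3.10 | 79.9% | 79.9% |
| Three quarters | 2.325 | 79.9% | 55.5% |
| Half | 1.55 | 79.9% | 28.8% |
| A quarter | 0.775 | 79.9% | 10.8% |
| None | 0 | 79.9% | 5.0% |

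**Step 4: check in the two-visit model.** The random-intercept model was simulated with 130 per arm and 2,000 runs. Assumptions not in the documents: residual SD 8.9 at both visits, within-person correlation 0.5, covariance treated as known.

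| True effect at 1 week / 12 weeks | β3 rejects | β3 + β4 rejects |
|---|---|---|
| 3.1 / 3.1 | 80% | 80% |
| 3.1 / 1.55 | 81% | 28% |
| 3.1 / 0 | 80% | 5% |
| 0 / 3.1 | 6% | 79% |

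The last row is the reverse error: with no effect at the primary time point, the named contrast still rejects in 79% of runs.

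**Step 5: at the stated enrolment.** The plan enrols 227 in total, not 2 × 145 = 290. That conflict is a separate matter, but 227 × 0.90 / 2 is about 102 completers per arm. There, β3 has 69.7% power for 3.1 points, and β3 + β4 has 23.6% if the effect has halved. The fall from 80% to 70% comes from the smaller sample, not from the contrast.

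**The case against.** The algebra is not in dispute. What can be said for the plan is this.

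- **The intent is plain.** The ranking sentence names 1 week as primary, β3 is in the model and any routine fit reports it, and the plan speaks of tests in the plural. It is fairer to say that no test of the 1-week effect is specified than that it could never be tested. This stands.
- **The word "This" is ambiguous.** It opens the test sentence and may refer to the 12-week outcome, mentioned last. The contrast is then correct. That removes the risk of a wrong contrast for the primary outcome, but leaves the primary outcome with no stated test. The text needs repair on either reading.
- **The power loss rests on an assumed decay.** This stands. Hypothesis 1 expects benefit at both visits, and with equal effects the two contrasts have equal power. The core of the point is that the contrast estimates a different quantity from the one declared primary; power shows what may follow.
- **The powers are approximate.** They use SD 8.9 without allowing for baseline adjustment, so they are illustrative.
- **The carry-over to Aims #2 and #3 is milder.** Those hypotheses are secondary and name both visits without ranking them. What they inherit is an unnamed 1-week contrast.

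**Conclusion.** The point holds. Under the stated coding, β3 + β4 is the 12-week group difference, and the declared primary 1-week difference is β3, for which the plan gives no test. This rests only on the plan's own model and coding.

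The practical size depends on the effect over time. At 130 completers per arm, with 3.1 points at 1 week, the power of the named contrast ranges from 80% (effect fully kept) through 29% (halved) to a 5% rejection rate (lost). An effect confined to 12 weeks would yield a positive "primary" result about 79% of the time. The two contrasts agree in expectation only if the effect is constant. The plan does not assume that, since it fits a Group×Time term and ranks the visits.

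Because this is the trial's confirmatory test, the wording must be corrected.

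**What to change.** Replace the test sentence under Aim #1, Hypothesis #1 with: *The primary test is of β3 = 0, the group difference at 1 week (Time = 0), at the two-sided 0.05 level. The secondary 12-week effect is tested by β3 + β4 = 0.*

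Make the same assignment explicit for the Aim #2 outcomes and the Stroke Impact Scale: β3 for 1 week, β3 + β4 for 12 weeks.

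The change is one sentence plus a cross-reference. It needs no new data and leaves the 145-per-group calculation as it is. It should be made and dated before anyone analyses outcomes by arm.

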| Measures to check fidelity (see section on Fidelity)/internal consistency   |  |            |
| Enactment (Translated)  | We will use Bakas, et al.,  survey and ask caregivers in the intervention to rate the amount and value of the information they received (see section on fidelity).  | <5 minutes |
| Used Resources Survey   | We will ask caregivers to disclose any resources they used to help them during the duration of the study.   | <3 minutes |

**Data Analysis:** Sample Size and Power Analysis: The sample will consist of 227 caregivers. Our pilot data showed 3.1 points reduction in CESD with a within group standard deviation of 8.9. Assuming such an intervention effect size on depression, 145 subjects per group would achieve 80% power to detect the difference at a 5% significance level. The sample size of 145 per group (intervention vs. standard care) was selected to account for the occurrence of a (10%) dropout rate. The 10% drop-out rate is a conservative estimate of attrition and is based on our pilot study led by our Collaborator [name]. The assumed effect size and variability were deemed reasonable based on a number of other sources. Radloff [66] described large changes pre and post treatment in a clinical setting, with depression from time of admission to 4 weeks post decreasing 20 points for “recovered” patients and 12 points for “still ill” patients. Grant et al.,[24] in a study of a telephone intervention to family caregivers of stroke caregivers, found an estimated 1 month treatment effect of 3.1.

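### The primary mixed model names only a random person effect; unless visit-specific variances are allowed, the single-visit standard errors will be biased if CES-D variance differs between 1 and 12 weeks

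*Combined protocol and SAP*

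**What the plan says.** In section 6, Data Analysis, Aim #1 – Hypothesis #1, a general linear mixed model "will be used to model the follow-up depression times (1 and 12 weeks post-intervention), adjusted for baseline scores as fixed effects". The fixed part contains baseline, time, group and group-by-time. Within-person correlation is handled "through the inclusion of a random person effect into the mixed model analysis".

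The tests of interest each concern one visit: "The primary outcome of interest will be the immediate post-intervention effect at 1-week post-intervention", with 12 weeks as a secondary outcome. Testing is "at two-sided 0.05 level".

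Neither this section nor Handling of Missing Data states a residual covariance structure, a variance for each visit, or a robust standard error. The text for Hypotheses #2 and #3 carries the same model over to burden, problem solving, self-efficacy, quality of life and the Stroke Impact Scale. The utilization counts have their own models and are not affected.

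The only variability figure is in the sample-size paragraph: "Our pilot data showed 3.1 points reduction in CESD with a within group standard deviation of 8.9".

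**The concern.** A random intercept with one residual variance implies that scores are equally variable at 1 and 12 weeks. A group difference at one visit should be judged against the variance at that visit. Under this model it is judged against a pooled value, so the standard error of the 1-week test depends partly on how spread out the scores are some 11 weeks later, and the reverse holds for the 12-week test.

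If the variances differ, one test becomes conservative and loses power, while the other rejects too often. The direction cannot be known in advance. The same assumption would also have to hold for every continuous scale that reuses the model.

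**Working it through.** **Inputs from the plan.** Difference 3.1 and SD 8.9 ("Our pilot data showed 3.1 points reduction in CESD with a within group standard deviation of 8.9"); two-sided alpha 0.05; "145 subjects per group would achieve 80% power to detect the difference at a 5% significance level"; the group size "was selected to account for the occurrence of a (10%) dropout rate"; "The sample will consist of 227 caregivers".

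**The plan's own figure.** n per group = 2 × (1.960 + 0.842)² × 8.9² / 3.1² = 129.4, rounded up to 130. Allowing for 10% dropout, 130 / 0.9 = 144.4, rounded up to 145. The stated 145 is reproduced. It rests on a single SD and says nothing about whether the SD differs by visit.

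**Assumptions that are not in the plan.** The SD of 8.9 is taken as the residual SD at 1 week (s1). The 12-week SD is s2 = r × 8.9, with r varied. Data are complete and the 227 participants are split equally.

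**Formulas.**
- Correct SE at visit j: sj × √(4/227) = sj × 0.1327.
- SE used under a random intercept with one residual variance, at both visits: p × 0.1327, where p = √((s1² + s2²)/2).
- Actual type I error at visit j: 2 × {1 − Φ(1.960 × p/sj)}.
- Power at visit j: Φ(3.1/SEj − 1.960 × p/sj), where SEj is the correct SE. With the correct variance, p/sj is replaced by 1.

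**Worked case, r = 1.2.** s2 = 10.68.
- p = √((79.21 + 114.06)/2) = 9.83.
- Correct SEs are 1.181 (1 week) and 1.418 (12 weeks). The SE used is 1.305, which is 10% too large at 1 week and 8% too small at 12 weeks.
- Type I error at 1 week: 2 × {1 − Φ(2.165)} = 3.0%. At 12 weeks: 2 × {1 − Φ(1.804)} = 7.1%.
- 1-week power: Φ(2.624 − 2.165) = 67.7%, against Φ(2.624 − 1.960) = 74.7% with the correct variance.

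**Range.**

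| r (12 wk / 1 wk) | SE used | Correct SE, 1 wk | Correct SE, 12 wk | Type I, 1 wk | Type I, 12 wk | 1-wk power, random intercept |
|---|---|---|---|---|---|---|
| 0.8 | 1.070 | 1.181 | 0.945 | 7.6% | 2.7% | 80.2% |
| 0.9 | 1.124 | 1.181 | 1.063 | 6.2% | 3.8% | 77.6% |
| 1.0 | 1.181 | 1.181 | 1.181 | 5.0% | 5.0% | 74.7% |
| 1.1 | 1.242 | 1.181 | 1.300 | 3.9% | 6.1% | 71.4% |
| 1.2 | 1.305 | 1.181 | 1.418 | 3.0% | 7.1% | 67.7% |

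With the correct variance, 1-week power is 74.7% in every row. The higher power at r below 1 comes from the inflated type I error. The type I errors depend only on r, not on the SD of 8.9 or on the sample size.

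**Simulation check.** The plan's model was fitted by REML with N = 227, an assumed within-person correlation of 0.6 and up to 10% of data missing completely at random (3,000 null runs for r of 1.0 to 1.2; 1,500 for r = 1.3 and for power).
- At r = 1.2, the random intercept rejected 3.0% (1 week) and 7.4% (12 weeks) under the null. The unstructured covariance rejected 4.7% at both. Power at 1 week was 66.6% against 73.1%.
- At r = 1.0, the mean 1-week SE was 1.212 (random intercept) and 1.211 (unstructured), with power 70.3% and 70.6%. These differences are within simulation error.
- Over r of 1.0 to 1.3, the unstructured model's type I error lay between 4.7% and 5.6% at both visits.

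**The case against.** The sentence about the random person effect concerns correlation. It does not state that the residual variance is constant, and visit-specific residual variances can sit alongside a random intercept. Only the fixed part of the model is written out. This objection stands: equal variance is the default reading of an incomplete specification, and the plan does not commit to it in words.

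The plan also contains no SD by visit, and nothing in it suggests that the spread changes between 1 and 12 weeks. A reader might infer that the planned standard errors are wrong as they stand. The documents do not support that: with equal variances they are correct. At a ratio of 1.1 they are off by only 4% to 5%.

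Finally, with time coded 1 at 12 weeks, the contrast that the plan names (β3 + β4) is the 12-week effect, although 1 week is declared primary. Until that is reconciled, it is open whether a given variance ratio would cost the primary test power or inflate its error rate. That is a separate matter, and so is the gap between 145 per group (290 in all) and the total of 227. Neither changes the case for freeing the covariance.

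**Conclusion.** The point holds in conditional form. The covariance is under-specified, and its usual reading ties two single-visit tests to an equal-variance assumption that the plan neither states nor supports with data. The resulting error is nil at equal SDs, small at a ratio of 1.1, and reaches about 7% to 8% actual type I error in one of the two tests at ratios of 1.2 or 0.8. The ratios are assumptions. The power figures also assume that 8.9 is the 1-week residual SD and that all 227 participants contribute data.

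This is a desirable improvement, not a flaw that undermines the trial. It is worth making because the remedy costs almost nothing and applies to every continuous outcome.

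**What to change.** In Aim #1 – Hypothesis #1, replace the random person effect with an unstructured 2x2 within-person covariance for the two follow-up scores, fitted by REML. Say that the continuous-outcome models under Hypotheses #2 and #3 use the same structure. The matrix should replace the random effect rather than be added to it, because two visits cannot support both.

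The cost is one sentence of text, one line of code and one more variance parameter (three instead of two). No loss of precision was measurable at N = 227 with equal variances. The choice of degrees-of-freedom method is immaterial at this sample size. The change should be fixed before outcome data are seen by group.

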**Data collection procedures:** Study personnel will follow a detailed, procedure manual, translated and adapted into Spanish from our previous pilot project, to collect the data. A data collector who is fluent in Spanish and has strong communication skills either in Gainesville or PR will be trained to conduct the assessments. Following enrollment and after going over the written statement script with eligible and interested study participants the data collector will contact caregivers at an agreed upon time to obtain demographic data and administer baseline survey questionnaires (see measures). To facilitate the collection of the baseline assessment, we will mail the demographic data form and questionnaires in advance for caregivers to read while the data collector asks questions and documents the caregivers' responses. We will also review the Veterans CPRS records and document the Veterans' age, gender, race/ethnicity, date/location/type of stroke, number of previous strokes, and resource use and any information related to the Veterans' care (treatments, medicines, patient and family education, case management, etc.). All caregivers who meet the study eligibility

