criteria and who are still willing to participate after completing the baseline assessment will be randomized to the intervention group or standard care group. All participants will complete two post-tests; post 1 will occur at approximately 9-10 weeks after enrollment (or 1-2 weeks after completion of the intervention for participants in the intervention group), and post 2 will occur approximately 12-13 weeks after post-test 1. The post-test assessments will include the same tools used in the baseline data collection. In addition, at both post-tests we will ask caregivers to disclose any resources they may have used during the duration of the study. At the 12 week post-test assessment the data collector will also ask questions on the Bakas “Enactment” tool to obtain data concerning the caregivers’ perceptions of the intervention. The data collector, who will be blinded to the group assignment of the caregivers, will telephone the caregivers to obtain the post-test assessments. We will obtain data on healthcare utilization since baseline assessment from the MCAS the Decision Support System National Data Extracts (DSS NDE) and the Non-VA Medical Carefee-basis files. Team members abstracting data from CPRS will be trained and inter-rater reliability testing will be conducted for all data collectors. We will conduct the assessments and intervention sessions at times that are convenient to the caregivers. All caregivers will receive reimbursement for their participation in the study.

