### Intervention

Participants in the intervention group will participate in 8 weekly telephone sessions with an interventionist. The telephone-based intervention consists of a problem-solving telephone support educational intervention led by a trained interventionist. The intervention’s main objective is to reduce caregiver burden and depressive symptoms by teaching caregivers a creative and optimistic approach to solving caregiving related problems. The intervention will utilize the problem solving module and refer to additional information/tools on the Spanish RESCUE website (<http://www.cidrr8.research.va.gov/rescue-espanol/>). The information included in the intervention consists of: 1. Introduction, 2. Illustrative Example, 3. Individualized Practice Exercise, and 4. Summary.

The intervention is adapted from the intervention used in our previous pilot project and based on the work of Bakas et al.,[23] who conducted a successful 8-week telephone intervention which used support approach and a task skill-building kit (TASK). In this proposed project we will tailor our pilot intervention to be culturally relevant for a Puerto Rican population. The intervention was developed to reflect specific characteristics of the target population such as language, cultural values and norms, and degree of acculturation. To enhance the cultural relevance of the intervention, we will use findings from our previous projects and guidelines from authoritative sources [55] that recommend: 1) involving persons from the target population in all phases of the project (e.g., Advisory Consortium), 2) emphasizing themes that are valued by the PR culture (e.g., family, religion, self-reliance), 3) assuring that the language and wording of on-line information is low-literate and appropriate by enlisting services of certified translators and Spanish-speaking experts, and 4) conducting the intervention and assessments by hiring research staff members (i.e., interventionist, data collector) who are Hispanic, fluent in Spanish, and knowledgeable about the PR culture. Research consistently shows that matching interventions to the individual needs of participants is more effective in engaging adults and modifying behaviors than prescriptive approaches.,[16] Other studies underscore the benefits of interventions and programs that are tailored to a specific race/ethnic populations.[55]

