### **Telephone/Internet Intervention: Topical Content**

|  |  |
|--|--|
| 
Topic 1: Introduction
 
Tour of the Spanish RESCUE Website and Orientation to the Problem-Solving Method (Session 1)
   | 
Step one: The interventionists will establish rapport with an "ice breaker" by asking the caregivers to talk about their families and what they enjoy doing at home.
 
Step two: The interventionists will review the content in the RESCUE workbook that the caregivers will have received in the mail. On the front of the workbook will be RESCUE stroke caregiver website logo, the URL, and the telephone # of the VA National Caregiver Support Line. Inside, the workbook will be the following: 1) directions for using the unique URL to access various materials on the RESCUE website, 2) details of the study with the name/phone numbers of the PI and PC, 3) calendar with the mutually-agreed dates and times for the intervention sessions and for the post-test assessment, 4) problem-solving diary, 5) copy of the written statement, 6) summary of the steps of the problem-solving approach for easy reference when the caregivers are away from their computers, and 7) a brief note thanking them for their participation accompanied by a motivational message to keep updating their plans. The interventionists will emphasize that the caregivers should only access the RESCUE website using their unique URLs, so we can track usage and gather study statistics.
 
Step three: The interventionists will tell the caregivers to log-onto the RESCUE website following directions in the workbook. The interventionists will give a tour of the various features on the RESCUE website as the caregivers simultaneously navigate and explore the website.
 
Step four: The interventionists will direct the caregiver to click on and open the problem-solving module (available on RESCUE website). Similar to how teachers use power-point presentations for classroom instruction, the interventionists will use the module to teach the problem-solving method.
 
Step five: The interventionists will discuss the basic premises of the problem-solving approach. Problems are successfully handled by developing a Creative and Optimistic way of thinking. The Problem-solving approach is effective and involves the following steps: 1) identifying & defining problems; 2) prioritizing problems; 3) selecting the highest priority problem; 4) gathering Expert information; 5) setting realistic goals; 6) listing all possible solutions; 7) choosing the best solution; and 8) evaluating the plan.
 
Step six: Prior to moving to the next part of the module, the interventionists will ask scripted questions to determine the caregivers' understanding and will clarify information as needed.
 |

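### Utilisation count models exclude baseline use on a mistaken ground, and the counting window is tied to intervention completion in one arm with no exposure offset

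*Combined protocol and SAP*

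**What the plan says.** Under Aim #3 - Hypotheses #3, utilisation (unintended bed days, emergency room visits, unscheduled clinic visits) is analysed by Poisson or negative binomial regression with a log link. On adjustment the plan says: "There will be no baseline covariates added to the model, as they are not applicable to the count measures". Later in the same paragraph it says that "all models will include covariates for prognostic factors deemed to have significant relationships with response and significant groupwise imbalances". The continuous outcomes, by contrast, are all adjusted for their baseline value.

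On the period counted: "Analyses will be conducted for the period following baseline to 12 weeks post-intervention assessments". Data collection procedures sets the dates: "post 1 will occur at approximately 9-10 weeks after enrollment (or 1-2 weeks after completion of the intervention for participants in the intervention group", with the second post-test about 12-13 weeks after the first. The Intervention section says: "Participants in the intervention group will participate in 8 weekly telephone sessions with an interventionist". The session table adds that each workbook holds a "calendar with the mutually-agreed dates and times for the intervention sessions and for the post-test assessment".

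On the data, the baseline record review covers "number of previous strokes, and resource use", with no look-back period stated. For the outcome the plan says "We will obtain data on healthcare utilization since baseline assessment". The Measures table has the number, dates and reasons of all visits recorded. I found no offset, person-time term or rule for shortened follow-up of the counts.

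**The concern.** Two separate points affect the same models.

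**Baseline use.** A count outcome can have a baseline count, and the planned models accept it like any other covariate. The stated reason for excluding it is therefore incorrect. The only remaining route for prior use is the rule that admits factors found to be both related to response and imbalanced. That rule is driven by the trial data, and the plan does not say whether prior use is eligible under it. The cost is precision on secondary outcomes for which no power is stated.

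**Counting window.** Without an offset, a log-link model compares counts per person, not rates. If one arm is observed for longer, its expected count rises even when the intervention does nothing. Completion of the intervention is an anchor in the intervention arm only. Hypothesis 3 predicts less utilisation in that arm. Slipped sessions would lengthen its window and work against the claim. Sessions that stop early, if treated as completion, would shorten it and favour the claim. The direction cannot be known in advance. Utilisation also feeds the budget analysis in Aim #4.

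**Working it through.** **The plan's own figures.** None exists for utilisation. The only power calculation is for the CES-D, and its 145 per group reproduces: a 3.1-point difference, SD 8.9, two-sided 5% and 80% power give 130 per group, and 130/0.9 rounds up to 145. The utilisation figures below therefore rest on assumed event rates, dispersion and correlations. The total of 227 is from the plan; equal allocation is assumed, giving about 113 per arm.

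**Nominal windows**
- Standard care: (9 to 10) + (12 to 13) = 21 to 23 weeks.
- Intervention: 8 weekly sessions + (1 to 2) + (12 to 13) = 21 to 23 weeks.
- Ratio at the midpoints: 22/22 = 1.00. As scheduled, there is no bias.

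**If the intervention arm slips.** With a constant rate and no true effect, the expected count ratio without an offset is (22 + slip)/22, so each week adds 1/22 = 4.5%. Rejection rates are simulated at mean 2 and dispersion 1 (1,500 replicates).

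| Average slip, whole arm | Count ratio | Rejection, no offset | Rejection, with offset |
|---|---|---|---|
| 0 weeks | 1.00 | 5.8% | 5.8% |
| 1 week | 23/22 = 1.045 | 6.4% | 5.9% |
| 2 weeks | 24/22 = 1.09 | 9.4% | 5.5% |
| 4 weeks | 26/22 = 1.18 | 18.0% | 6.1% |

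An analytic check uses SE² = (1/μ₀ + k)/n + (1/μ₁ + k)/n. For a 4-week slip with n = 113.5, the SE is 0.160 and ln(1.18)/SE is about 1.04, giving 18.0% rejection. For 2 weeks it gives 8.4%. At mean 0.6 (700 replicates), a 4-week slip gives 15% without an offset and 7% with one. Across means 0.5 to 4 and dispersions 0.5 to 2, the analytic range is about 6-12% for 2 weeks and 10-31% for 4 weeks.

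**If sessions stop early.** If 20% stop after session 4 and this counts as completion, the ratio is (22 - 0.2 × 4)/22 = 0.964. Rejection stays at about 6%.

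**If follow-up is truncated.** A death at mid-window removes half of that person's time, so each percentage point of difference in deaths between arms shifts the ratio by about 0.5%.

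**Value of adjusting for prior use.** Assumed: 113 per arm, control mean 2, dispersion 1, true rate ratio 0.70, 26-week look-back. The unadjusted SE is √[(1/2 + 1)/113 + (1/1.4 + 1)/113] = 0.169, against 0.168 in simulation (1,000 replicates per cell). Power is Φ(0.357/SE - 1.96), where 0.357 = |ln 0.70|; unadjusted, it is 56%.

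| Pre/post rate correlation | Adjusted SE | Fall in SE | Analytic power | Simulated power, unadjusted to adjusted |
|---|---|---|---|---|
| 0.3 | 0.165 | 2% | 58% | 57 to 57% |
| 0.5 | 0.160 | 5% | 61% | 55 to 58% |
| 0.7 | 0.152 | 10% | 65% | 58 to 67% |
| 1.0 (constant rates) | 0.129 | 23% | 79% | 56 to 81% |

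At the same four correlations the SE falls 1%, 3%, 6% and 12% at mean 1, and 0.6%, 1.5%, 3% and 6.5% at mean 0.6. A second simulation with a different frailty model (means 0.5 to 2, frailty variance 1 to 2) gave variance reductions of 0-3%, 2-13% and 6-33% at correlations 0.3, 0.6 and 0.9.

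**The case against.** The other side has a fair case on weight.

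- **Reading of the sentence.** Set against Hypothesis 1, the excluded covariate is most naturally the baseline value of the same outcome, and prior use might still enter as a prognostic factor. That route exists. But it depends on observed significance and imbalance, does not name prior use, and sits awkwardly beside the exclusion. The text needs repair on either reading.
- **No like-for-like baseline.** The outcome is unintended or unscheduled use settled by consensus review, whereas a look-back would be all-cause. Eligibility requires a stroke within the last year, and the Tampa site screens for inpatients with new-onset stroke, so prior use may be dominated by the index admission. This stands as a practical limit. The simulations do not model such a proxy, so the real gain could be smaller than shown.
- **Small gain.** At correlations of 0.3 to 0.5 the fall in SE is 5% or less. The 23% figure needs constant rates, which is doubtful soon after a stroke. Dispersion 1 is not shown to suit bed days.
- **The window.** The completion clause may only restate the 9-10 weeks, and agreed calendar dates should limit slip. Nothing in the plan suggests a 4-week average slip. Utilisation comes from records under a consent waiver, so caregiver dropout need not end follow-up, and the end-of-life exclusion should keep deaths few. All of this makes the bias conditional. It does not tell the analyst when the window closes if sessions run late or are never completed.

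These points limit the importance of the concern; they do not remove it.

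**Conclusion.** The concern holds on both points, at the level of a change that should be made to secondary analyses. The stated ground for excluding baseline use is incorrect. Its consequence is lost precision only: a 2-10% larger-than-necessary SE (as a fall from the unadjusted value) at mean 2 and correlations of 0.3 to 0.7, and about 3% or less at mean 0.6.

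The window is equal by design (ratio 1.00), but it is not protected against differential timing. The risk is slight for a slip of a week and material only if the whole arm slips by several weeks. Its direction cannot be predicted. Confidence is medium, because the plan documents no utilisation rate, dispersion, correlation or delay.

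**What to change.** 1. Delete the sentence excluding baseline covariates from the count models.
2. Count events over one fixed window from randomisation in both arms, for example 22 weeks, using the visit dates already to be recorded. Include an offset of log(days at risk), ending at death or loss of records.
3. Prespecify prior use as a covariate, entered as log(1 + count) over a fixed pre-enrolment look-back such as 26 weeks. Use unadjudicated all-cause emergency visits, clinic visits and bed days from the same records as the outcome. Exclude the index stroke admission or add a time-since-stroke term. State that prior use enters by prespecification, whatever the observed imbalance.

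The cost is a change of analysis wording and a modest extra record extraction for up to 227 Veterans. There is no added participant contact, and unadjudicated counts avoid repeating the consensus review. There are two drawbacks: the precision gain may be small where events are rare, and the fixed window will close before the 12-week interview for caregivers whose sessions slip.
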